7.1 Sample Size Determination

Unpublished data at our institution reveals an 60% incidence of esophageal spasm-related pain. We assume that magnesium might decrease the incidence of esophageal spasm-related pain by 30%. Based on this assumption, our calculation show that 45 patients in each group would be necessary to acquire statistical significance, with a two-sided $\alpha = 0.05$ and $\beta = 0.20$. Considering a 10% dropout rate, 50 patients are necessary for each group.

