7.2 Statistical Methods

Data will be expressed as means \pm SD, number (proportion), relative risk, 95% CI, absolute risk reduction, or number needed to treat.

The primary outcome is the incidence of esophageal spasm-related pain at 0 h postoperatively, compared using the chi-square test.

The secondary outcomes of the incidence of esophageal spasm-related pain at 24 hours postoperatively, intraoperative opioid usage, postoperative opioid consumption, and discharge opioid prescription will be compared using the chi-square test or Fisher's exact test as appropriate. Continuous variables will be compared using the Mann–Whitney *U* test. Categorical variables will be compared using the chi-square test or Fisher's exact test as appropriate.

Post hoc subgroup analyses will be conducted regarding the incidence of esophageal spasm-related pain according to achalasia type (e.g. type 1, 2, or 3), preoperative H2-receptor antagonist use, preoperative proton pump inhibitor use, and intraoperative opioid usage. *Post hoc* subgroup analysis will be further conducted on postoperative magnesium levels and the incidence of esophageal spasm-related pain at 24 hours.

All *P* values will be two-sided, and a value of $P < 0.05$ will be considered statistically significant.

Comparisons of postoperative pain between the two groups at time 0 h and time 24 h will be analyzed using the Mann–Whitney *U* test and performed using an adjusted significance level of 0.0125 (0.05/4) after *post hoc* analysis using the Bonferroni method.

Statistical analyses will be performed using R version 4.0.3.

CONFIDENTIAL

This document is confidential and the property of Stanford University School of Medicine.

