7.3 Subject Population(s) for Analysis

Enrollment will cease when the target sample size is obtained. Analyses will be performed on an intention-to-treat basis. All patients who are enrolled and randomly allocated for treatment will be included in the analysis.

8 Safety and Adverse Events

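### Do the 45 per group and the primary chi-square test need a written-out magnesium-arm incidence and a stated continuity correction?

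*Combined protocol and SAP*

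**What the plan says.** All of this is in the combined protocol and SAP.

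- **Section 7.1, control rate:** "Unpublished data at our institution reveals an 60% incidence of esophageal spasm-related pain".
- **Section 7.1, effect:** "magnesium might decrease the incidence of esophageal spasm-related pain by 30" per cent. The scale and the resulting magnesium-arm incidence are not given.
- **Section 7.1, size:** "45 patients in each group would be necessary to acquire statistical significance", at two-sided alpha 0.05 and beta 0.20. A 10% dropout allowance raises this to 50 per group. No formula or program is named for the calculation.
- **Section 7.2, primary test:** "The primary outcome is the incidence of esophageal spasm-related pain at 0 h postoperatively, compared using the chi-square test". P values are two-sided and judged against 0.05. No section mentions a continuity correction.
- **Section 7.2, summaries and software:** the results may be expressed as "relative risk, 95% CI, absolute risk reduction, or number needed to treat", and "Statistical analyses will be performed using R version 4.0.3".
- **Section 7.3, population:** "All patients who are enrolled and randomly allocated for treatment will be included in the analysis".
- **Section 4.4.2, withdrawals:** apart from magnesium levels kept with permission, a withdrawn subject's data are destroyed.

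**The concern.** Two inputs to the primary comparison are not written down.

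The first is the effect size. Taking 30% off 60% gives 30% if the reduction is absolute and 42% if it is relative. Section 7.2 reports on both scales, so the wording alone does not decide. If the relative reading were meant, 45 per group would be far too few.

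The second is the version of the test. The Pearson chi-square and its Yates-corrected form can give P values on opposite sides of 0.05 for the same table. If the version were chosen after the results were seen, the primary conclusion could depend on that choice. It could shift only towards significance, because the correction always shrinks the statistic. Naming R without a function or option does not settle which version is meant.

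**Working it through.** **Inputs.** Control incidence 0.60, alpha 0.05 two-sided (z = 1.960), power 0.80 (z = 0.842), 45 per group before dropout and 10% dropout (section 7.1). Allocation is 1:1 (section 5.3). The magnesium incidence is 0.30 or 0.42, depending on the reading.

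**Step 1: the plan's own figures.** The dropout step reproduces: 45 / (1 − 0.10) = 50. For the 45 itself, take p1 = 0.60, p2 = 0.30, difference d = 0.30 and mean 0.45. The usual formula, with pooled variance under the null and unpooled under the alternative, is

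n = [1.960 × √(2 × 0.45 × 0.55) + 0.842 × √(0.60 × 0.40 + 0.30 × 0.70)]² / 0.30²

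= (1.379 + 0.565)² / 0.09 = 41.97, so 42.

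The continuity-corrected size is (n/4) × [1 + √(1 + 4/(n × d))]². With n = 41.97 this gives 48.41, so 49.

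| Formula, 60% vs 30% | Uncorrected | Corrected |
|---|---|---|
| Unpooled variance | 39.24 (40) | 45.67 (46) |
| Arcsine | 41.79 (42) | – |
| Pooled null, unpooled alternative | 41.97 (42) | 48.41 (49) |
| Pooled in both terms | 43.17 (44) | 49.61 (50) |

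No formula here returns exactly 45. It lies between the uncorrected range (40 to 44) and the corrected range (46 to 50), so the formulas alone do not show which version was used.

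**Step 2: which scale.** For 60% versus 42% the variance-based formulas in the table give 118 to 122 per group uncorrected and 129 to 132 corrected. Exact uncorrected power at 45 would be only 38.6%. The stated 45 is therefore compatible with the absolute reading and not with the relative one.

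**Step 3: exact power for 60% vs 30%.** Every possible 2×2 table was enumerated with its binomial probability, and each version was compared with the 0.05 critical value.

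| Per group | Pearson | Yates | Versions disagree |
|---|---|---|---|
| 45 | 81.8% | 75.3% | 6.5% |
| 48 | 85.4% | 80.1% | 5.4% |
| 50 | 87.6% | 82.9% | 4.7% |

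Power first reaches 80% at 41 per group for Pearson (81.3%; 79.6% at 40) and at 48 for Yates (80.05%; 78.5% at 47). The stated 80% at 45 holds for the uncorrected test only.

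**Step 4: false positives and a borderline table.** If both incidences are 60%, the versions disagree in 2.1% of trials at 45 per group and 2.0% at 50. Type I error at 50 is then 5.2% for Pearson and 3.2% for Yates. Over all common incidences from 0.01 to 0.99, the maximum at 50 per group is 5.69% for Pearson and 3.52% for Yates.

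Take 30/50 with pain on control and 20/50 on magnesium. Pearson gives 4.00 (p = 0.0455) and Yates gives 3.24 (p = 0.0719). With 19/50 on magnesium both are significant (p = 0.0278 and 0.0455). The choice is worth one patient at that margin.

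**Step 5: are the cells large enough for the uncorrected test?** With a mean incidence of 0.45, the smallest expected count is 0.45 × 45 = 20.25 at 45 per group and 0.45 × 50 = 22.5 at 50. Small cells give no reason to expect a correction.

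**The case for a change.** The strongest case for acting is that the primary claim rests on one P value against 0.05 and the plan does not say in full how to compute it. One sentence would close the gap at almost no cost. Disagreement also becomes more likely if the true effect is smaller than planned: it is 8.0% at 60% versus 42%, at 45 and at 50 per group. And the assurance that 100 patients suffice does not hold equally for both versions. Section 7.3 includes everyone randomised, but section 4.4.2 destroys withdrawn subjects' outcome data, and section 7.1 itself allows for 10% dropout. At that loss 45 per group remain, and Yates power is 75.3%. Yates needs 48 of 50, so losses could not exceed 2/50 = 4%.

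These figures stand. They show that the corrected version would not deliver the planned power at the planned dropout. That supports reading the plan as uncorrected; it does not show that the plan is in error. The test, its two-sidedness, the threshold and the software are all set in advance. A correction is normally named when it is intended, and on the plain reading sections 7.1 and 7.2 agree. The fact that only Pearson is significant in every discordant table follows from the algebra of the correction and is not evidence about this trial.

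**Conclusion.** No change to the plan follows. The missing scale resolves itself, because 45 per group fits 60% to 30% and excludes 60% to 42%. The missing test version is a detail that an analyst can fill sensibly: the uncorrected Pearson test is the plain meaning of the wording and the version that meets the stated 80% at the stated 45 (81.8%, rising to 87.6% if all 50 per group are evaluable). No stated figure or rule is shown to be wrong, and the estimated risks, their ratio and their difference are the same under either version.

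What is at stake is the 4.7% to 6.5% of trials under the planned effect, and about 2% under no effect at 60%, in which the two versions would disagree.

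The conclusion rests on two readings: the reduction is absolute, and the test is uncorrected. If Yates were used, the planned 100 would keep 80% power only with losses of about 4% or less. The exact origin of the 45 remains unknown, since none of the formulas tried returns it exactly; this does not affect the conclusion, because exact uncorrected power at 45 exceeds 80%.

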7.2 Statistical Methods

Data will be expressed as means \pm SD, number (proportion), relative risk, 95% CI, absolute risk reduction, or number needed to treat.

The primary outcome is the incidence of esophageal spasm-related pain at 0 h postoperatively, compared using the chi-square test.

The secondary outcomes of the incidence of esophageal spasm-related pain at 24 hours postoperatively, intraoperative opioid usage, postoperative opioid consumption, and discharge opioid prescription will be compared using the chi-square test or Fisher's exact test as appropriate. Continuous variables will be compared using the Mann–Whitney *U* test. Categorical variables will be compared using the chi-square test or Fisher's exact test as appropriate.

Post hoc subgroup analyses will be conducted regarding the incidence of esophageal spasm-related pain according to achalasia type (e.g. type 1, 2, or 3), preoperative H2-receptor antagonist use, preoperative proton pump inhibitor use, and intraoperative opioid usage. *Post hoc* subgroup analysis will be further conducted on postoperative magnesium levels and the incidence of esophageal spasm-related pain at 24 hours.

All *P* values will be two-sided, and a value of $P < 0.05$ will be considered statistically significant.

Comparisons of postoperative pain between the two groups at time 0 h and time 24 h will be analyzed using the Mann–Whitney *U* test and performed using an adjusted significance level of 0.0125 (0.05/4) after *post hoc* analysis using the Bonferroni method.

Statistical analyses will be performed using R version 4.0.3.

CONFIDENTIAL

This document is confidential and the property of Stanford University School of Medicine.

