Duration of administration	Only limited to surgery duration, from start of mucosal incision to patient extubation
Reference therapy	Reference is placebo (normal saline)
Statistical Methodology	Chi-square test to compare primary outcome (postoperative pain) Chi-square test, Fisher's exact test, or Mann-Whitney U test to compare secondary outcomes (intraoperative opioid usage, postoperative opioid usage, pain at 24 hours, esophageal symptoms questionnaire results)

CONFIDENTIAL

This document is confidential and the property of Stanford University School of Medicine.

1 Introduction

This document is a protocol for a human research study. This study is to be conducted according to US and international standards of Good Clinical Practice (FDA Title 21 part 312 and International Conference on Harmonization guidelines), applicable government regulations and Institutional research policies and procedures.

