1.5 Dose Rationale and Risk/Benefits

The magnesium bolus dosing of 50 mg/kg emulates the dose used in a recent urologic study that explored the effect of magnesium to decrease bladder catheter-associated discomfort.⁹ Furthermore, this bolus dose and the infusion rate are the most frequently reported dose/rate in a meta-analysis of 20 randomized controlled trials.¹² The aforementioned meta-analysis found no major adverse events associated with magnesium toxicity, whilst finding a statistically and clinically significant decrease in postoperative pain. The medication is administered intravenously as part of the intraoperative anesthetic regimen. The POEM surgery lasts on average 1 to 2 hours, which is the maximum duration of the magnesium infusion. This will limit the risk of magnesium toxicity. Hence, the study will be safely investigating a nonopioid analgesic that has been shown to be efficacious in similar populations undergoing a diverse range of surgeries, with the hope of clarifying the antispasmodic potential of magnesium.

2 Study Objectives

Primary Objective

To assess the efficacy of magnesium sulfate on decreasing esophageal spasm-associated pain as measured by subjective pain scores and the esophageal symptoms questionnaire score.¹⁴

Secondary Objective

To assess the efficacy of magnesium sulfate on decreasing intraoperative opioid usage.
 To assess the efficacy of magnesium sulfate on decreasing postoperative opioid consumption.
 To assess the efficacy of magnesium sulfate on decreasing discharge opioid prescription.
 To assess the efficacy of magnesium sulfate on decreasing postoperative pain as measured by the esophageal symptoms questionnaire score at 24 hours.

3 Study Design

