3.2 Primary Study Endpoints

This study will evaluate the efficacy of magnesium sulfate on decreasing esophageal spasm-associated pain as measured by subjective pain scores and the esophageal symptoms questionnaire score.

CONFIDENTIAL

This document is confidential and the property of Stanford University School of Medicine.

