3.3 Secondary Study Endpoints

This study will assess the efficacy of magnesium sulfate on decreasing intraoperative opioid usage, postoperative opioid consumption, discharge opioid prescription, and on decreasing postoperative pain as measured by the esophageal symptoms questionnaire score at 24 hours.

4 Subject Selection and Withdrawal

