6.2 Day of surgery

- 6.2.1 In the preoperative holding area, all enrolled patients will have preoperative plasma calcium and magnesium levels drawn and complete the esophageal symptoms questionnaire (ESQ), a validated survey to assess symptoms of dysphagia, globus, and reflux.

6.2.2 The patient will proceed to the OR for anesthetic care.

- 6.2.2.1 Patients will undergo rapid sequence induction of general anesthesia. In the control group, the anesthesia team will use ketamine, propofol, succinylcholine, and esmolol and/or opioids at their discretion. In the treatment arm, the anesthesia team will use ketamine and propofol using lean body weight (LBW) dosing, and succinylcholine at total body weight (TBW) dosing. After endotracheal tube placement and confirmation, sevoflurane in air and oxygen will be used for maintenance of general anesthesia. The anesthesiologist will ensure adequate neuromuscular relaxation throughout the case.

- 6.2.2.2 In the treatment arm, the anesthesia team will prepare a magnesium sulfate infusion within a 20 ml syringe. Patients will receive a magnesium sulfate bolus of 50 mg/kg lean body weight over 15 minutes, followed by a magnesium sulfate infusion at 25 mg/kg/hr when the endoscopist begins mucosal incision. In addition, the patients will receive dexamethasone 0.1-0.2 mg/kg at the start of case, and ondansetron 4 mg at the end of case. The magnesium infusion will be discontinued at extubation. After surgery, patients will be admitted to the postanesthesia care unit. For mild pain reported as a numeric score ranging from 1 to 3, acetaminophen 1000 mg IV will be offered. For pain greater than a score of 3, opioids (fentanyl and hydromorphone) will be available. For nausea and vomiting, prochlorperazine and haloperidol will be provided. Calcium gluconate and a code cart with emergency drugs and airway equipment will be made available in case of symptoms concerning for magnesium toxicity.

- 6.2.2.3 In the control arm, the anesthesia team will prepare a normal saline infusion within a 20 ml syringe. Patients will receive a normal saline bolus of 50 mg/kg lean body weight over 15 minutes, followed by a normal saline infusion at 25 mg/kg/hr when the endoscopist begins mucosal incision. Opioids (fentanyl and hydromorphone) will be administered for analgesia at the discretion of the anesthesia team. In addition, patients

CONFIDENTIAL

This document is confidential and the property of Stanford University School of Medicine.

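### The primary endpoint is stated in conflicting ways, and the supplied text does not say what makes a case of spasm-related pain or when 0 h is

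*Combined protocol and SAP*

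**What the plan says.** **Statistical plan.** Section 7.2: "The primary outcome is the incidence of esophageal spasm-related pain at 0 h postoperatively, compared using the chi-square test". Section 7.1 plans on a 60% incidence from unpublished institutional data and a decrease of 30%, with no case definition or time point. It arrives at 45 per group, or 50 after 10% dropout.

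**Objective and endpoint sections.** Section 2 gives the primary objective: "To assess the efficacy of magnesium sulfate on decreasing esophageal spasm-associated pain as measured by subjective pain scores", and adds the ESQ score. Section 3.2 repeats this: "as measured by subjective pain scores and the esophageal symptoms questionnaire score".

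**Synopsis.** The Statistical Methodology row has "Chi-square test to compare primary outcome (postoperative pain") and lists among the secondary outcomes "pain at 24 hours, esophageal symptoms questionnaire results". The Objectives row hypothesises a reduction in the severity of postoperative pain.

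**24 h secondary.** Section 3.3 has "decreasing postoperative pain as measured by the esophageal symptoms questionnaire score at 24 hours". Section 7.2 has the incidence of spasm-related pain at 24 hours.

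**Procedures.** Section 6.2.1 describes the ESQ as "a validated survey to assess symptoms of dysphagia, globus, and reflux". It is given before surgery, in the PACU once nursing judges recovery sufficient (6.3), and on the morning of POD1 (6.4.1). The only numeric pain score in Section 6 is an analgesia trigger in the treatment-arm text (6.2.2.2): "For mild pain reported as a numeric score ranging from 1 to 3". The control-arm text (6.2.2.3) has no such score.

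**The concern.** Two analyses of different kinds can each claim to be the primary: a score analysis under Sections 2 and 3.2, and a yes/no analysis under 7.2. A report could present either one and cite the protocol for it.

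Choosing 7.2 does not settle the matter. The supplied text does not say what pain score or ESQ response makes a case, how spasm pain is told apart from other pain after the procedure, or when 0 h falls. If those choices are not fixed in writing elsewhere, they remain open when the data are analysed. The 60% planning rate also cannot be tied to the variable that will be analysed, because its own definition and timing are not given.

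**Working it through.** **1. The statements of the primary, side by side.**

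| Place | Variable | Type | Time | Test |
|---|---|---|---|---|
| Synopsis, Objectives | severity of postoperative pain | graded | none | none |
| Synopsis, Statistical Methodology | postoperative pain; ESQ secondary | implied categorical | none | chi-square |
| Sections 2 and 3.2 | pain scores plus ESQ score | scores | none | none |
| Section 7.1 | incidence of spasm-related pain | binary | none | not named |
| Section 7.2 | incidence of spasm-related pain | binary | 0 h | chi-square |

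Pain scores could be the instrument behind an incidence, so scores against incidence is not by itself a strict contradiction. The role of the ESQ is: it is part of the primary in Sections 2 and 3.2 and secondary in the synopsis.

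**2. Can the tested variable be obtained from Section 6?** It needs a yes/no spasm-pain status at 0 h in both arms. Section 6 schedules the ESQ, whose described content does not name pain, at a PACU time that is not fixed. No rule links an ESQ response or a pain score to yes or no. The same holds at 24 h, and the morning of POD1 is not necessarily 24 h after surgery.

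**3. What the planning figures support.** Inputs from Section 7.1: control rate 0.60, two-sided alpha 0.05, power 0.80, 45 per group. The 30% decrease is not labelled absolute (60% vs 30%) or relative (0.60 × 0.70 = 42%).

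Pooled normal approximation, with p̄ the mean of the two rates:

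Power = Φ{[|p1 − p2|√n − 1.960√(2p̄(1 − p̄))] / √(p1(1 − p1) + p2(1 − p2))}

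*The plan's own figure, absolute reading.* Here p̄ = 0.45, 1.960√(2 × 0.45 × 0.55) = 1.3790 and √(0.24 + 0.21) = 0.6708. For 80% power, n = (1.3790 + 0.8416 × 0.6708)² / 0.30² = 41.97, so 42 per group; with continuity correction it is 49. The stated 45 lies between the two and is not reproduced exactly. The dropout step does reproduce: 45 / 0.90 = 50.

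*Power at 45, absolute reading.* 0.30√45 = 2.0125, and (2.0125 − 1.3790) / 0.6708 = 0.944, so power is 82.8%. Summing exact binomial probabilities over all outcomes gives 81.8% for the uncorrected chi-square and 75.3% with continuity correction.

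*Power at 45, relative reading.* Here p̄ = 0.51, 1.960√(2 × 0.51 × 0.49) = 1.3856, √(0.24 + 0.2436) = 0.6954 and 0.18√45 = 1.2075. Then (1.2075 − 1.3856) / 0.6954 = −0.256, so power is 39.9%; 80% power would need 120 per group.

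*Primary in Section 3.2.* No mean, SD or effect size is given for pain scores or the ESQ score, so no power can be computed.

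**The case against.** The strongest reply is that the statistical plan is clear about which outcome is primary. Section 7.2 names one outcome, one time and one test, 7.1 powers an incidence, and the synopsis assigns a chi-square. On this view, Sections 2 and 3.2 only name the instruments. Much of this stands, and it is why the fix keeps the 7.2 endpoint. It does not explain the ESQ being in the primary in two sections and secondary in the synopsis, and it supplies no rule from score to case. No statement says that 7.2 prevails over 3.2.

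A second reply is that the CRF (9.3) and the attachments (Section 15), which are not in the supplied text, may hold a pain item, a definition or a timing. That cannot be excluded. They would still leave 3.2 and 7.2 in conflict.

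Three stronger readings are not supported:

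- *That spasm pain will not be recorded.* The PACU ESQ is the evident early assessment, and numeric pain scoring is implied by the analgesia text.
- *That the primary is tested at 0.0125.* Section 7.2 ties that level to Mann–Whitney comparisons after post hoc Bonferroni analysis; 0.05 is the natural level for the chi-square. The remaining fault is one of labelling: the sentence names one measure at two times, for which 0.05 / 2 = 0.025, but divides by 4.
- *That the sample size is shown to be adequate, or inadequate.* Either claim needs a choice between absolute and relative, and on continuity correction, that the documents do not make.

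**Conclusion.** The point holds and should be fixed before analysis. The contradiction concerns the trial's one confirmatory endpoint, and following the text exactly does not lead to a single primary analysis. The firm core is the ESQ's double role and the absence, in the supplied text, of a rule that produces the yes/no outcome at a defined 0 h. The 24 h secondary is split in the same way.

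No loss of power or shift in event rate can be attributed to the missing definition from the documents. The power range in the working (82.8%, exact 75.3% with continuity correction, or 39.9%) shows only what 45 per arm buys under different readings of Section 7.1, assuming that the 60% rate applies to the endpoint finally adopted. The conclusion about the endpoint does not depend on which reading is right.

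**What to change.** 1. Make incidence of spasm-related pain at 0 h (chi-square, two-sided 0.05) the single primary in the synopsis (Objectives and Statistical Methodology rows) and in Sections 2, 3.2, 7.1 and 7.2. Make ESQ scores secondary.
2. In 7.1 and 7.2, state the case definition and time point that produced the 60% rate, including how spasm pain is told apart from other postoperative pain. If another definition is adopted, restate 7.1 for it. Say there whether the 30% is absolute or relative, and in 7.2 whether the chi-square is continuity-corrected.
3. In 6.3 and 6.4.1, for both arms, chart a time-stamped yes/no item with a 0–10 score. Define 0 h and 24 h, each with an allowed window, and record the time of any earlier PACU analgesia.
4. Add 24 h incidence to 3.3.
5. Label the Mann–Whitney comparisons at 0.0125 as secondary, and make the divisor match the comparisons listed.
6. Reconcile the PACU analgesia texts in 6.2.2.2 and 6.2.2.3, which differ by arm.

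**Cost.** Wording, plus four charted fields (yes/no, score, time, earlier-analgesia time) at up to two time points: at most 4 × 2 = 8 per patient, or 800 for 100 patients. It is wording only if the CRF already holds them. The number of patients changes only if restating 7.1 requires it.

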5.4 Preparation and Administration of Study Drug

The anesthesia team will prepare the study treatment based on the instructions within the envelope. Specifically, the anesthesia team will be instructed to draw up 10 g (20 ml) of the study drug within a 20 ml syringe, or to draw up 20 ml of normal saline within a 20 ml syringe. Although both medications are colorless and transparent, and thus are indistinguishable to the endoscopist, the syringes will be labeled as “study” to minimize drug error during the intraoperative anesthetic management. These medications will be administered using a syringe pump (Alaris; Becton, Dickinson and Company, New Jersey, USA) available in all SHC operating rooms. Instructions to manually program the syringe pump will be provided.

Specifically, the anesthesia team will be instructed to enter 10 g of the study drug in 20 ml of volume, and to enter the patient’s lean body weight. The team will enter the infusion rate as 25 mg/kg/hr, and save these settings.

When the endoscopist announces that she/he will start the mucosal incision, the syringe pump will be programmed to bolus 50 mg/kg over 15 minutes. After the bolus is administered, the syringe pump will default to the infusion rate of 25 mg/kg/hr. The anesthesia team will stop the infusion at extubation.

CONFIDENTIAL

This document is confidential and the property of Stanford University School of Medicine.

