5.6 Prior and Concomitant Therapy

Information on their preoperative medications will be collected, including use of multivitamins, herbal supplements, or magnesium-containing supplements, and use of acid-reducing medications such as H2-receptor antagonists or proton pump inhibitors.

During the study, the patients will be expected to receive standard anesthetic care including hypnotics, narcotics, neuromuscular blockers (e.g. succinylcholine/rocuronium), antiemetics, vasopressors, antihypertensives, and anesthetics as needed at the anesthesia team's discretion. In the rare case of magnesium toxicity, all healthcare providers will have access to calcium chloride/gluconate therapy to reverse the cardiorespiratory and musculoskeletal effects.

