8.4 Unblinding Procedures

Postoperative magnesium levels evaluated after surgery will reveal those among study participants who received magnesium or normal saline. If a study participant experiences a serious adverse event postoperatively, including cardiorespiratory arrest, unblinding will occur to ensure the patient's safety by evaluating if the patient would benefit from administration of calcium chloride therapy. The patient's randomization envelope contents will be shared with the care team. Documentation of this will be indicated in our data collection spreadsheets. The sponsor will be notified of each participant who was unblinded within 24 hours by phone or email, followed by a written narrative of the event within 48 hours.

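### Section 7.2 plans a pain subgroup by intraoperative opioid usage, which is a post-randomisation secondary endpoint; separately, the tests listed for the ESQ ignore the preoperative score

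*Combined protocol and SAP*

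**What the plan says.** **Opioid subgroup.** Section 7.2 plans *post hoc* subgroup analyses of the incidence of spasm-related pain by achalasia type, preoperative H2-receptor antagonist use, "preoperative proton pump inhibitor use, and intraoperative opioid usage". Section 3.3 makes the last of these an efficacy endpoint: "This study will assess the efficacy of magnesium sulfate on decreasing intraoperative opioid usage". The Study Summary hypothesises that magnesium lowers perioperative opioid requirements.

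**Who gives the opioids.** Under section 5.6, "the patients will be expected to receive standard anesthetic care including hypnotics, narcotics" and other agents as the anesthesia team sees fit. Section 5.4 says of that team: "The anesthesia team will prepare the study treatment based on the instructions within the envelope". Section 5.8 names only the endoscopist and the patient as blinded. Sections 6.2.2.1 and 6.2.2.3 give the control arm discretionary intraoperative opioids. The treatment-arm text in 6.2.2.1 and 6.2.2.2 mentions no opioid before the PACU.

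**Magnesium level.** Section 7.2 adds that "subgroup analysis will be further conducted on postoperative magnesium levels and the incidence of esophageal spasm-related pain at 24 hours". It does not say whether the arms are pooled. Section 8.4 states: "Postoperative magnesium levels evaluated after surgery will reveal those among study participants who received magnesium or normal saline".

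**ESQ.** It is completed before surgery (6.2.1), in the PACU (6.3) and on the morning of POD1 (6.4.1). The Study Summary lists "Chi-square test, Fisher's exact test, or Mann-Whitney U test to compare secondary outcomes", and counts ESQ results among those outcomes. Section 7.2 never names the ESQ; for continuous variables it gives the Mann-Whitney test.

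**The concern.** A subgroup analysis of a randomised trial keeps its causal reading only if the subgroup is fixed before treatment. Suppose magnesium reduces opioid use, and some patient factor, such as pain sensitivity, drives both opioid need and later pain. Magnesium patients who still received opioids are then, on average, needier than control patients who did. Magnesium patients who received none include some who would have needed opioids on control. In both strata the magnesium group has the worse prognosis, and magnesium looks harmful or ineffective even if it does nothing to pain. Calling the analysis *post hoc* does not remove this.

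The magnesium-level analysis can mislead in another way. If the level largely identifies the arm, a pooled comparison of high with low levels shows the arm difference again and could be read as dose-response.

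For the ESQ, a randomised comparison without baseline adjustment is valid. What is lost is precision and protection against chance imbalance, although the baseline score is already collected.

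**Working it through.** **Inputs from the plan.** Control pain 60% (7.1). Per-arm size 50, which is 45/(1 − 0.10) (7.1). Loading dose 50 mg/kg over 15 minutes, then 25 mg/kg/hr, for an expected 1 to 2 hours (5.2, 5.4). No stated figure in the plan depends on this point.

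**Assumed inputs.** Opioid use, the strength of the shared factor, the agreement between level and arm, and the ESQ correlation are not in the documents, so ranges are shown.

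**1. Bias within opioid strata.** Let U ~ N(0,1) be the shared factor, with

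- logit P(opioid | U, arm) = a_arm + bU
- logit P(pain | U, opioid) = c + g·opioid + bU

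The arm has no direct effect on pain, and c is set so that control pain is 60%. Writing p_O and p_Y for these two probabilities, pain among opioid recipients in an arm is E[p_O(U)·p_Y(U)] / E[p_O(U)]. For non-recipients p_O is replaced by 1 − p_O. The expectations were computed by Gauss-Hermite integration.

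Magnesium minus control, in percentage points, with g = 0 (opioid stratum / no-opioid stratum):

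| b | 58.5% vs 37.5% use | 58.5% vs 19.8% use | 58.5% in both |
|---|---|---|---|
| 0 | 0 / 0 | 0 / 0 | 0 / 0 |
| 0.5 | +1.1 / +1.1 | +2.1 / +2.1 | 0 / 0 |
| 1 | +3.3 / +3.7 | +6.3 / +6.6 | 0 / 0 |
| 1.5 | +5.4 / +6.4 | +10.0 / +11.4 | 0 / 0 |
| 2 | +6.8 / +8.9 | +12.3 / +15.7 | 0 / 0 |

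The all-randomised difference is 0 in every cell, so the non-zero entries come only from stratifying. If opioids also relieve pain (g = −0.5), the stratum bias hardly moves: +1.1 to +9.0 and +2.0 to +15.5 for b from 0.5 to 2. The overall difference then becomes +1.8 to +2.4 and +3.1 to +4.3, because less opioid is given.

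**2. Noise in the same comparison.** The standard error of a stratum difference is √[p_M(1 − p_M)/n_M + p_C(1 − p_C)/n_C], where n is 50 times the stratum's share of the arm. For b from 0.5 to 2 and g = 0 it is 11.7 to 14.3 points at 37.5% use and 12.9 to 17.7 at 19.8%.

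**3. Pooled magnesium level.** Suppose a high/low split agrees with arm in a fraction A of patients, arms are equal in size, and level is unrelated to pain within arm. The high-minus-low contrast is

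[A·p_M + (1 − A)·p_C] − [(1 − A)·p_M + A·p_C] = (2A − 1)(p_M − p_C).

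For A = 80%, 90% and 100% it returns 60%, 80% and 100% of the arm difference.

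**4. Infusion duration.** Counting from the start of the bolus, the per-kg dose is 50 + 25 × 0.75 = 68.75 mg/kg at 1 hour and 50 + 25 × 1.75 = 93.75 mg/kg at 2 hours. Duration fixes the per-kg dose, so adjusting a level analysis for duration would remove the dose variation under study.

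**5. ESQ precision.** Relative to an unadjusted mean difference, ANCOVA multiplies the variance by 1 − ρ², where ρ is the pre/post correlation. The equivalent size for 100 patients is 100/(1 − ρ²).

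| Assumed ρ | Variance factor | As if n = |
|---|---|---|
| 0.1 | 0.99 | 101 |
| 0.3 | 0.91 | 110 |
| 0.5 | 0.75 | 133 |
| 0.7 | 0.51 | 196 |

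**The case against.** **The plan does not say that arms are compared within opioid strata.** True: 7.2 names no contrast or test, and a description of pain by opioid use would also fit. But comparing arms within levels is what a trial subgroup analysis ordinarily means, and this variable stands in one list with three baseline factors. If something else is intended, 7.2 should say so. The bias argument applies only to arm comparisons.

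**The magnitudes are assumptions, and the bias is mostly below one standard error.** Both statements are correct. At 37.5% use the bias never exceeds its standard error; at 19.8% it does so only at b = 2 in the no-opioid stratum. This limits how often a single result would mislead, but the error is systematic and a wide interval does not make the estimate interpretable.

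**The arm-specific regimens in 6.2.2 may leave almost no opioid users on magnesium.** This is a fair addition. At an assumed 2% use, the same model gives a user-stratum standard error of about 24 to 48 points, so that comparison is not usefully estimable. This strengthens the case against the subgroup. It also means that opioid use as an outcome may partly reflect the assigned regimen. Sections 5.6 and 6.2.2 differ on this and must be reconciled.

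**The ESQ point is an efficiency preference.** Largely so. Unadjusted analysis is valid, Mann-Whitney on change scores is not excluded (though nowhere stated), and 1 − ρ² is relative to a mean difference, not to Mann-Whitney. The gain is small if ρ is low. The suggestion still stands because the data are already collected.

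**Conclusion.** The concern holds. Intraoperative opioid usage is a post-randomisation endpoint under the control of an unblinded team, and arm comparisons within its levels are not randomised comparisons. They are biased if magnesium changes opioid use, as the trial hypothesises, and a common factor drives opioid need and pain. Under the assumed range the bias is roughly 1 to 16 points against magnesium, and it is zero if either condition fails. The true size cannot be learned from the documents.

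The magnesium-level point is conditional on pooling: if arms are pooled, the result mostly repeats the arm contrast. The ESQ point concerns precision only, and its value depends on an unknown correlation.

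The primary chi-square test, the sample size and the intention-to-treat set are untouched. The change should be made before the data are analysed, but it does not bear on the primary conclusion.

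**What to change.** In section 7.2:

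1. **Remove intraoperative opioid usage as a subgroup factor and keep it as an outcome.** Analyse achalasia type, H2-receptor antagonist use and proton pump inhibitor use with treatment-by-factor interaction tests. Label them exploratory and note their low power with about 100 patients. State how patients with a motility disorder other than achalasia are classified.
2. **Do not pool magnesium level across arms.** Present it against 24-hour pain within the magnesium arm only, as an exploratory, non-randomised description. Report infusion duration alongside, but do not require adjustment for it.
3. **Name the ESQ analysis.** Compare PACU and POD1 scores by ANCOVA or proportional-odds regression on arm and preoperative ESQ, choosing one in advance, and report the adjusted difference or odds ratio with its 95% CI. Sections 2 and 3.2 place the ESQ in the primary endpoint while 7.2 makes pain incidence primary, so settle its role at the same time.

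The cost is SAP wording and standard R regression code, with no new data. The plan takes on a modest modelling assumption for the ESQ and loses one exploratory subgroup.
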